3.6.2 Imputations in relation to analyses

The variable DTYPE will be used to mark imputed values. Imputation of missing data will be based on the measurements included in the analysis.

3.6.3 Missing baseline

For any missing baseline value, the last value prior to baseline visit should be used. However, any measurements assigned to a visit at or before baseline, but with an assessment date after first drug date will not be used as a baseline measurement.

The value will be assigned to the baseline visit and the record will be marked with DTYPE='LVPD' (Last Value Prior Dosing). If no value exists prior to the baseline visit, the baseline value should be kept as missing.

Statistical Program. SpecificationETrial ID: NN2211-4232VUTN: U1111-1170-7035SEudraCT No: 2015-002417-29P	Date:10 September 2019Version:1.0Status:FinalPage:18 of 42	Novo Nordisk
---	--	--------------

The values assigned to a baseline visit will be included in the in-trial period (APHASE/APERIODC="Treatment" and INTRFL='Y'), even though the sample date will be prior to randomisation.

For subjects who are randomised at another date than the randomisation visit date the randomisation date will be set to the randomisation visit date.

3.6.4 Definition of treatment/trial completers

Treatment and trial completers are defined directly in the CRF by the investigator. A subject has completed trial if subject completes 104 weeks of treatment.

3.6.5 Treatment emergent events

A Treatment Emergent Adverse Event (TEAE) is defined as an event with onset or increase in severity on or after the time of first trial product administration and no later than seven days (7 times 24 hours) after the time of last trial product administration.

A Treatment Emergent hypoglycaemic episode is defined as an event with onset on or after the time of first trial product administration and no later than one day (24 hours) after the time of last trial product administration.

If the date and datetime of the event is not missing or is partial, the exact number of hours since trial product administration is used to determine if the event is treatment emergent. This also means that an event on the same date as trial product administration will not be treatment emergent if the time of the event is before time of trial product administration.

However, if the start-date and datetime for the adverse event or hypoglycaemic episode is missing or partial, and an imputed date or datetime can result in an onset of the event that is within the treatment emergent period, then the event is defined as treatment emergent. Otherwise it is defined as non-treatment emergent. Following partial date and datetime rules should be applied:

- If the time of the event is partially observed such that only the hours are observed, the event is regarded as treatment emergent if the date and hour of the event is the same as for the trial product administration or if the treatment-emergent window extends to at least the beginning of the given hour.
- If the time (hours) of the event is missing the event is regarded as treatment emergent if it occurs on the date of trial product administration or no later than the specified amount of time after this date.
- If date is missing or partial missing the event is not regarded as treatment emergent.

Statistical Program. Specification		Date:	10 September 2019	Novo Nordisk
Trial ID: NN2211-4232	CONFIDENTIAL	Version:	1.0	
UTN: U1111-1170-7035	CONFIDENTIAL	Status:	Final	
EudraCT No: 2015-002417-29		Page:	19 of 42	

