17.4.1.2 Safety endpoints

The following secondary endpoints are used to support the safety objectives:

Protocol		Date:	04 September 2015	Novo Nordisk
Trial ID: NN2211-4232	CONFIDENTIAL	Version:	1.0	
UTN: U1111-1170-7035	CONFIDENTIAL	Status:	Final	
EudraCT no.: 2015-002417-29		Page:	52 of 67	

- Number of severe hypoglycaemic episodes
- Number of severe or blood glucose confirmed symptomatic hypoglycaemic episodes
- Number of documented symptomatic hypoglycaemic episodes (ADA)
- Number of SAEs
- Number of AEs leading to permanent discontinuation of trial product
- Change from baseline at 104 weeks or at premature treatment discontinuation:
 - o Lipids
 - Biochemistry
 - Haematology
 - o Pulse

Adverse events

The collected AEs will be coded using the most recent version of the Medical Dictionary for regulatory Activities (MedDRA) coding. A treatment emergent adverse event (TEAE) is defined as an event that has onset date (or increase in severity) on or after the first day of trial product administration and no later than seven days after the last day of trial product administration.

AE data will be displayed in terms of the number of subjects with at least one event, the percentage of subjects with at least one event, the number of events and the event rate per 1000 patient years of exposure. The main AE summaries will only contain TEAEs. Non-treatment emergent AEs will be included in listings and overview summaries.

Hypoglycaemic episodes

The endpoints involving hypoglycaemic episodes will be analysed separately using a negative binomial regression model with the number of treatment emergent episodes as response, the logarithmic function as link function and the logarithm of the time period in which episodes are considered treatment emergent as offset. The model will include treatment arm as factor and baseline HbA_{1c} as a covariate. The results will be described by the rate ratio for the comparison of Victoza[®] versus OAD and the associated 95% confidence interval and two-sided p-value.

The hypoglycaemic episodes will also be summarised descriptively in a similar way as the AEs in terms of the number of subjects with at least one event, the percentage of subjects with at least one event, the number of events and the event rate per 1000 patient years of exposure.

Classification of Hypoglycaemia:

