4.2 Data dependencies

4.2.1 Execution order

The execution order of some data derivations is crucial. The following selected data derivation rules apply in the given order:

- Partial date/time imputation.
- Laboratory LLOQ/ULOQ conversion.
- Reference range indicators
- Define ANELFL based on
 - o Fasting status
 - Visit reallocation
 - o Re-test
 - Last observed value before or at first drug date carried forward to baseline
- Setting observation period record flags, and other period variables

In the datasets with a visit structure (BDS) there should only be one record per subject per visit per parameter after the data derivations at this time (for ANELFL='Y').

- Endpoints calculation: BMI, , hypoglycaemia etc.
- Trial specific endpoints calculation
- Calculate values for variables relative to baseline
- Imputations in relation to analyses, e.g. Last values carried forward

In case of several derivations for a given parameter at a given visit, the DTYPE will be the last derivation in the order above. The variable DDCOM will show all derivations for the given parameter and visit, as e.g. 'LOQHALF | LOCF from AVISITN=110'.

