5.2.8 ADHYPO – Hypoglycaemic episode analysis

The ADHYPO contains data on all reported hypoglycaemic episodes for randomised subjects. All events from the first trial-related activity after the subject has signed the informed consent until the end of the post-treatment follow-up period are included. Data is built on SDTM data XH, SUPPXH, RELREC, and information from ADSL.

The ONTRTFL defines the on-treatment period for hypoglycaemic episodes as described in section 2.3.3. The TRTEMFL defined the on-treatment period with an addition of 1 more day (section 3.6.5).

The variables ACAT1 contains the analysis category 1 of ADA hypoglycaemic classification described in protocol. Each of the ADA classification categories are also marked in the variable flags ADASYMFL, ADDOCSFL, ADPROBFL, ADPSEUFL, ADSEVFL, ADUNCLFL, ADUNNSFL.

The variables ACAT2 contains the analysis category 1 of NN hypoglycaemic classification described in protocol. Each of the NN classification categories and merged categories are also marked in the variable flags NNASCOFL, NNCONFL, NNSECOFL, NNSEVFL, NNSYCOFL, NNSYSEFL, NNUNCLFL.

The date-time imputations follow the derivation rules in 3.6.1, and note that missing time information imputed to 00:00 implies that the hypoglycaemic episodes are imputed to occur during day-time.

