5.2.9 ADHYPOEN – Hypoglycaemic episode analysis endpoint

The ADHYPOEN contains data on the number of treatment emergent severe hypoglycaemic episodes for all FAS subjects.

The counts are made over two periods: on-treatment or on-treatment+1 day, corresponding to ONTRFL='Y' and TRTEMFL='Y', respectively, in ADHYPO. This results in two rows per subject; one with the count for the on-treatment period with ONTRFL='Y' and TRTEMFL='' and one with the count for the on-treatment+1 day period with ONTRFL='' and TRTEMFL='Y'.

A binary variable indicating whether there are >0 or 0 episodes are also included using the CRIT1/CRIT1FL structure.

Statistical Program. Specification		Date:	10 September 2019	Novo Nordisk
UTN: U1111-1170-7035 EudraCT No: 2015-002417-29	CONFIDENTIAL	Version: Status: Page:	1.0 Final 32 of 42	

Endpoint	Topic code (PARAMCD)	Technical details
Severe hypoglycaemic	HYPO_N_TE_SEVERE	Sum of records with
episodes	(SEV_HYPO)	ADHYPO.ADSEVFL="Y"
		and
		ADHYPO.TRTEMFL="Y"
Severe or blood glucose	HYPO_N_TE_NNSBCFL	Sum of records with
confirmed symptomatic	(HYCNFSEX)	ADHYPO.NNSECOFL="Y"
hypoglycaemic episodes		and
		ADHYPO.TRTEMFL="Y"
Documented symptomatic	HYPO_N_TE_DOC_SYMP	Count of records where
hypoglycaemic episodes	(DOC_HYPO)	ADHYPO.TRTEMFL = "Y"
(ADA)		and ADHYPO.ACAT1 =
		"Documented symptomatic
		hypoglycaemia"

Table 15Derived hypoglycaemic endpoints

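### SAP 3.6.5 gives two opposite treatment-emergent rules for events with a missing or partial start date, and nothing in the protocol or SAP says which one applies

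*SAP*

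**What the plan says.** SAP 3.6.5 sets the treatment-emergent window: from first trial product administration to 7 days (adverse events) or 1 day (hypoglycaemic episodes) after the last. For a missing or partial start date, its general paragraph makes the event treatment emergent if "an imputed date or datetime can result in an onset of the event that is within the treatment emergent period", and otherwise not. A lead-in then says that partial-date rules are to be applied, and three bullets follow. The first two cover incomplete times. The third covers incomplete dates: "If date is missing or partial missing the event is not regarded as treatment emergent".

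Other places bear on the point:

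- SAP 3.6.1, Table 8, imputes partial start dates. An adverse event goes to the first of the month, moved to treatment start if that is later. A hypoglycaemic episode goes to day 1, or to treatment start if it falls in the same month.
- SAP 4.2.1 puts "Partial date/time imputation" first in the derivation order.
- SAP 5.2.8 says of hypoglycaemic episodes: "The date-time imputations follow the derivation rules in 3.6.1". It refers to 3.6.5 for the treatment-emergent flag, TRTEMFL.
- SAP 5.2.9, Table 15, requires that flag for all three hypoglycaemia counts.
- Protocol 17.4.1.2 defines treatment emergence by onset and has no exclusion for incomplete dates. It also says: "The main AE summaries will only contain TEAEs".

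**The concern.** The general paragraph expressly includes incomplete start dates. The third bullet excludes all of them without condition, so for these events the paragraph has no effect. Two programmers working from 3.6.5 could produce different safety tables and both claim to have followed the SAP.

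Treatment-emergent status decides entry to the main adverse event summaries. Through TRTEMFL it also decides the response in the hypoglycaemia models, which the protocol describes as a "negative binomial regression model with the number of treatment emergent episodes as response". Compared with the general paragraph, the bullet can only remove events. Some of those events certainly began on treatment, because the known month and year lie wholly inside the window.

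**Working it through.** The plan gives no figure to reproduce. The check compares the rules on concrete dates and then illustrates the size.

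**1. The two rules on month-only dates.** Assumed for illustration: first dose 10 March 2017, last dose 20 September 2017. The adverse event window ends 20 + 7 = 27 September; the hypoglycaemia window ends 20 + 1 = 21 September.

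| Known start | General paragraph with Table 8 date | General paragraph, any possible day | Third bullet |
|---|---|---|---|
| Feb 2017, adverse event | Yes (moved to 10 March) | No | No |
| Feb 2017, hypoglycaemia | No | No | No |
| Mar 2017, either | Yes (10 March) | Yes | No |
| May 2017, either | Yes (1 May) | Yes | No |
| Sep 2017, either | Yes (1 September) | Yes | No |
| Oct 2017, either | No | No | No |

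The rules conflict whenever the imputed date falls in the window. May 2017 is the plainest case: every possible day is on treatment, so the event meets the protocol definition, yet the bullet excludes it. The February adverse event is a separate weakness of Table 8, which moves a start known to precede treatment onto the first-dose date.

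**2. How often the known month settles the matter.** Share = (days in calendar months wholly inside the window) / (days in the window), assuming uniform onset. In the example, April to August gives 30 + 31 + 30 + 31 + 31 = 153 days. The adverse event window has 22 + 153 + 27 = 202 days, so the share is 153/202 = 76%. The hypoglycaemia window has 22 + 153 + 21 = 196 days, so the share is 153/196 = 78%.

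Averaging the share over 366 consecutive first-dose dates (from 1 March 2016, an arbitrary choice), with the window running from first dose to the end of week W plus 7 days, gives for adverse events:

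| Weeks on treatment (W) | 4 | 8 | 16 | 38 | 104 |
|---|---|---|---|---|---|
| Share certainly on treatment | 18% | 54% | 76% | 89% | 96% |

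For hypoglycaemia (plus 1 day) the shares are 89% at week 38 and 96% at week 104.

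Other assumed onset patterns, with 38 weeks of treatment, give lower shares:

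- first 28 days: 48%;
- last 30 days: 71% (adverse events) and 54% (hypoglycaemia);
- last 14 days: 48% and 28%.

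**3. Effect on a count.** If a fraction p of the events that would otherwise be treatment emergent has an incomplete start date, the count falls from N to N(1 − p). The documents give no p. For assumed values of 1%, 2% and 5%, the count falls by 1%, 2% and 5%.

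**The case against.** The strongest case for the other side has four parts.

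- **The bullets are the operative instructions.** The lead-in says they are to be applied, and a specific rule can be read as prevailing over a general one. This is a fair reading, and the SAP is not silent on how to proceed. But the bullets are presented as carrying out the paragraph. The first two do so; the third cancels it for incomplete dates. That is not a stated order of precedence.
- **The bullet may cover only dates still incomplete after imputation.** Imputation comes first in 4.2.1. The adverse event start row of Table 8 gives no rule for a missing month or year, so the bullet would keep some content. This may be what was meant. The text does not say so, and the bullet also names partial dates, which include the day-missing dates that Table 8 imputes.
- **The PSPS may settle it.** SAP 1.1 places the programming specifications there, and that document was not supplied. This limit stands.
- **Few events will be involved.** Only serious adverse events, those leading to permanent discontinuation, and medical events of special interest are collected. SAEs must be entered within 24 hours, and the hypoglycaemia form asks for date and time. This also stands, and it keeps the point minor.

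A reader might infer that Table 8 and the derivation order prove the inclusive rule was intended. They lean that way, but neither says that an imputed date decides treatment-emergent status, and imputed starts also serve other purposes such as event duration (SAP 3.6.6).

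**Conclusion.** Wrong as written, minor severity. SAP 3.6.5 contradicts itself for incomplete start dates, and nothing in the supplied documents resolves it. Applied literally, the third bullet removes events known to have started on treatment, contrary to protocol 17.4.1.2.

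The number of affected events is unknown and probably small. The calendar shares are shares of that unknown number and rest on assumed onset patterns.

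Three stronger readings are not supported:

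- **That nearly all day-missing dates are certain to be on treatment.** The 89% to 96% range needs 38 weeks or more of treatment and uniform onset. Subjects who stop early have much lower shares, and adverse events leading to discontinuation are one of the collected types.
- **That the treatment comparison is biased.** The rule is the same in both arms, and no document suggests that incomplete dates would be more frequent in one of them.
- **That efficacy results are affected.** The primary endpoint does not use this flag. SAP 5.2.14 builds the hypoglycaemia-free responder endpoints from episodes between treatment start and the analysis date, without naming TRTEMFL. Excluded adverse events also remain in listings and overview summaries.

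**What to change.** 1. Delete the third bullet of SAP 3.6.5 and keep one rule: an event with a missing or partial start date is treatment emergent unless the known part of the start date, or a stop date before first dose, shows that onset was outside the window.
2. State in 3.6.5 that exact hours apply only when date and time are both complete. As worded, that sentence also takes in partial dates.
3. In the adverse event row of Table 8, move an imputed start to the first-dose date only when the known month and year include that date and the stop date is not before first dose. The hypoglycaemia row already limits the move to the same month.

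The stop-date condition is needed. Without it, an adverse event with start March 2017, stop 5 March 2017 and first dose 10 March 2017 would count as treatment emergent although it had ended before treatment.

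The cost is one bullet, one sentence, one table row and the matching program lines, plus a check against the PSPS. The downside is small: a few events with wholly unknown dates will be counted as treatment emergent, which is the cautious direction for safety.

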3.6.6 Durations

Durations are calculated as Duration (in years) = $\frac{\text{End of period-Start of period + 1}}{365.25}$

Table 9Duration variables and related period definitions

Duration periods	Flag	Start of period	End of period	Duration variable
Exposure		TRTSDT	TRTEDT	TRTDURY
In trial	INTRFL	RANDDT	EOSDT	INTRDURY
(Observation				
time)				
On treatment	ONTRTFL	TRTSDT	TRTEDT	ONTRDURY
Duration of AE		ASTDT	AENDT	AEDURN,
				AEDURU
Duration of		Diagnosis of	RANDDT	DIABDURY
diabetes		diabetes		

3.6.7 Age

AGE is the age in SDTM, and AAGE is the calculated age:

$$AAGE = \frac{Date \ of \ visit - Date \ of \ birth + 1}{365.25}$$

The age group 1 defined by the two variables AAGEG1BL and AAGEG1BN is defined as described in Table 10.

Table 10Definition of AAGEG1BL and AAGEG1BN

AAGEG1BL	AAGEG1BN
$18 \le age < 45$ years	10
$45 \le age < 55$ years	20
$55 \le age < 65$ years	30
$65 \le age < 75$ years	40
$75 \le age < 85$ years	50
$85 \leq age$	60

The age group 2 for EudraCT is defined by the two variables AAGEG2BL and AAGEGE2BN is defined as described in Table 11.

Table 11Definition of AAGEG2BL and AAGEG2BN

CONFIDENTIAL

Date: Version: Status: Page:

AAGEG2BL	AAGEG2BN
$18 \le age < 65$ years	10
$65 \le age < 85$ years	20
$85 \leq age$	30

In the age calculation, no rounding should be done to preserve the precision of days.

3.6.8 Body Mass Index (BMI)

BMI will be calculated as: Weight(kg) / Height²(m^2) even if the BMI is collected on the CRF.

Table 12Definition of BMIG1BL and BMIG1BLN

BMIG1BL (kg/m^2)	BMIG1BLN
< 25	10
25 - <30	20
30 - <35	30
35 - <40	40
>= 40	50

3.6.9 Rounding

Data points stored in numeric variables in datasets will not in any circumstances be rounded. Rounding will only occur if numeric variables are converted to character information, e.g. in CTR outputs as a final step when presenting numeric data. In this case, number of decimal points will follow the table shells.

3.6.10 Fasting status

According to the protocol fasting plasma glucose (FPG) at visit 2, 4, 6, 8, and 12 are required to be taken when subjects are fasting.

Any of the above measurements taken when the subjects are non-fasting will be excluded from the analyses and have ANELFL ='' and ANELREA='Record was excluded due to subject being non-fasting'.

All other assessments do not require a fasting status.

3.6.11 Laboratory lower and upper limit of quantification

When laboratory data are below the lower limit of quantification (LLOQ), i.e. the collected value contains "<", the reported value is converted to half of the LLOQ value. Laboratory values above

Statistical Program. Specification
Trial ID: NN2211-4232
UTN: U1111-1170-7035
EudraCT No: 2015-002417-29

CONFIDENTIAL

Date: Version: Status: Page:

upper limit of quantification (ULOQ), collected value containing ">", is set to the ULOQ value. The variable DTYPE will be used to mark converted laboratory data, 'LOQHALF' and 'ULOQ'.

Any analysis imputations (see section 3.6.2) will be made on the converted numeric data.

LOQ can be identified by LB.LBORRES containing "<" or ">". The conversion should happen in ADaM by updating AVAL based on the rule and setting DTYPE = "LOQHALF" or DTYPE="ULOQ1". AVALC should be left empty for these records. LBORRES and LBORRESU should be included in the dataset for traceability. Comment:

3.6.12 Time-to-event endpoints

3.6.12.1 Primary endpoint - Time to inadequate glycaemic control

The primary endpoint is the time to inadequate glycaemic control defined as $HbA_{1c} > 7.0\%$ (53 mmol/mol) at two scheduled consecutive visits after first 26 weeks of treatment and up to 104 weeks. First possible occurrence is at week 38.

The data will inherently be interval censored, since HbA_{1c} is only measured at the scheduled visits while subjects may reach an $HbA_{1c} > 7.0\%$ at any time between 2 visits. The possible failure times will be viewed as continuous variable which can only be observed to lie in the interval between the visit when the treatment failure is established and the previous scheduled visit.

In order to perform the analysis, interval (t1, t2] will be identified where t1 is the time of the last visit at which an event has not occurred for the subject and t2 is the time of the visit at which the event occurs.

HbA_{1c} records will be extracted from the laboratory analysis dataset (ADHBA1C) with a selection on non-missing measurements which were taken while on treatment at the scheduled visits 5, 6, 7, 8, 9, 10, 11 and 12 which correspond to weeks 16, 26, 38, 52, 65, 78, 91 and 104.

The first post-baseline HbA1c assessment was done at visit 5 (Week 16). However, for determining consecutive visits, assessments from visit 6 onwards will be considered.

Visits with only non-missing measurements of HbA_{1c} will be considered to determine whether visits are consecutive or whether a visit is the last visit on treatment. For example, if there are HbA_{1c} measurements at visit 6 and visit 8 but it is missing at visit 7, then visit 6 and 8 will be considered as two consecutive visits.

The interval (t1, t2] will be identified as below.

1) If the subject discontinued treatment before Week16, subject is censored with t1 as time of visit at Week 0 and t2 as missing.

Statistical Program. Specification		Date:	10 September 2019	Novo Nordisk
Trial ID: NN2211-4232	CONFIDENTIAL	Version:	1.0	
UTN: U1111-1170-7035	CONFIDENTIAL	Status:	Final	
EudraCT No: 2015-002417-29		Page:	22 of 42	

- 2) If the subject discontinued treatment between Week 16 and Week 26, then subject is censored with t1 as time of visit at Week 16 and t2 as missing.
- 3) If the subject does not have any non-missing HbA_{1c} measurements on treatment, subject is censored with t1 as time of visit at Week 0 and t2 as missing.
- 4) If there are two consecutive measurements of $HbA_{1c} > 7.0\%$ taken at Week26 or later, then event has occurred with t1 as time of first measurement of $HbA_{1c} > 7.0\%$ and t2 as time of second measurement of $HbA_{1c} > 7.0\%$.
- 5) If last available HbA_{1c} measurement is at Week 26 or later but before Week104 and the value is > 7.0%, then the event has occurred with t1 as time of last available measurement and t2 as time of next visit. If the next visit has not happened then, t2 will be time of next planned visit as per protocol defined intervals between the visits.
- 6) If last available HbA_{1c} is between Week 26 and Week 104 and the value is $\leq 7.0\%$, then the subject is censored with t1 as time of last available measurement and t2 as missing.
- 7) If last available HbA_{1c} is at Week 104 and there are no consecutive visits with HbA_{1c} > 7.0%, then the subject is censored with t1 as time of visit at Week104 and t2 as missing.

Figure 1 Identification of interval (t1, t2]

The time to inadequate glycaemic control will be compared between the Victoza[®] arm and the OAD arm using a two-sided non-parametric test at a 5% significance level. The test will be a generalised log rank test for interval censored failure time data, not based on any model assumptions such as proportional hazards or adjusted for any covariates.

The result of the log rank test will be presented as the asymptotic p-value obtained from a chisquare distribution.

3.6.12.2 Secondary endpoint - Time to premature treatment discontinuation (for any reason including inadequate glycaemic control)

The secondary endpoint is the time to premature treatment discontinuation (for any reason including inadequate glycaemic control).

The data will inherently be interval censored, since the criteria for treatment discontinuation is primarily checked at the scheduled visits while subjects may have discontinued treatment at any time between 2 visits. The possible event time will be considered as a continuous variable.

For subjects that discontinued treatment before Week 104, due to inadequate glycaemic control, interval (t1, t2] will be identified as mentioned in the section 3.6.12.1.

For subjects that discontinued treatment before Week 104, due to any other reason, interval (t1, t2] will be identified where t1 is the time of the last attended visit on treatment and t2 is the time of the next planned visit.

The subjects that completed the treatment for Week 104 and did not meet inadequate glycaemic control criteria before Week 104 will be considered as censored,

The time to premature discontinuation (for any reason including inadequate glycaemic control) will be compared between the Victoza[®] arm and the OAD arm using a two-sided non-parametric test at a 5% significance level. The test will be a generalised log rank test for interval censored failure time data, not based on any model assumptions such as proportional hazards or adjusted for any covariates.

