8.1.5 Withdrawals

If a subject is withdrawn from the trial, the investigator must aim to undertake procedures similar to those for visit 12 as soon as possible if acceptable to the subject. The end-of-trial form must be completed, and final drug accountability must be performed even if the subject is not able to come to the trial site. In addition the follow-up telephone contact (visit 13) should be completed approximately 1 week after the early treatment discontinuation visit if possible. After that the case book must be signed.

Although a subject is not obliged to give his/her reason(s) for withdrawing from a trial, the investigator must make a reasonable effort to ascertain the reason(s), while fully respecting the subject's rights. Where the reasons are obtained, the primary reason for not completing the trial must be specified on the end-of-trial form in the eCRF.

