17.4 Secondary endpoints

17.4.1 Supportive secondary endpoints

17.4.1.1 Efficacy endpoints

Time to premature treatment discontinuation (for any reason including inadequate glycaemic control)

Protocol Trial ID: NN2211-4232 UTN: U1111-1170-7035 EudraCT no.: 2015-002417-29

CONFIDENTIAL

Date: Version: Status: Page:

The time to premature treatment discontinuation will be analysed using the same type of generalised log rank test as for the primary endpoint with the difference that subjects who discontinue treatment before 104 weeks without having an event of inadequate glycaemic control will not be considered as censored but as meeting the endpoint. For these discontinued subjects, the event will be considered to have occurred in the interval between the last attended visit on treatment and the next planned visit.

Change from baseline in HbA_{1c} at 104 weeks or at premature treatment discontinuation

The change from baseline in HbA_{1c} will be evaluated using an analysis of covariance (ANCOVA) model where the last post-baseline measurement taken on treatment will enter as the dependent variable, treatment arm and country as factors and baseline HbA_{1c} as a covariate. The estimated differences between Victoza[®] and OAD will be presented together with the corresponding 95% confidence intervals and two-sided p-values.

To further describe the effects of Victoza[®] compared to OAD with respect to the change from baseline in HbA_{1c}, supportive analyses will be performed using a mixed model for repeated measurements (MMRM) where all post-baseline measurements taken on treatment will enter as the dependent variable, treatment arm as a factor and baseline HbA_{1c} as a covariate. The factor and the covariate will be nested within visit. An unstructured covariance matrix for the measurements within subject will be employed. From this analysis, the differences between Victoza[®] and OAD at different visits will be estimated.

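### SAP 3.6.12.2 sorts discontinuers by reason rather than by result, so an unconfirmed stop recorded as inadequate glycaemic control could be censored, contrary to protocol 17.4.1.1

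*SAP*

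**What the plan says.** SAP 3.6.12.2 divides subjects who stop treatment before week 104 into two groups by why they stopped. For the first group, "due to inadequate glycaemic control, interval (t1, t2] will be identified as mentioned in the section 3.6.12.1". The second group, those who stopped for any other reason, has the event between the last attended on-treatment visit and the next planned visit. The section then names one set of censored subjects: those who completed 104 weeks without meeting the control criteria.

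The section it refers to, SAP 3.6.12.1, has seven rules. Rule 1: "If the subject discontinued treatment before Week16, subject is censored with t1 as time of visit at Week 0 and t2 as missing". Rule 2: "If the subject discontinued treatment between Week 16 and Week 26, then subject is censored with t1 as time of visit at Week 16". Rule 3 covers subjects with no non-missing HbA1c "measurements on treatment, subject is censored with t1 as time of visit at Week 0 and t2 as missing". Rule 6 censors a subject whose last value, between weeks 26 and 104, is 7.0% or below. Rules 4 and 5 give events. SAP 5.2.13 sets the censoring flag to 0 if an event is met and 1 otherwise.

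Protocol 17.4.1.1 uses a different split. A subject who stops before week 104 without an event of inadequate glycaemic control "will not be considered as censored but as meeting the endpoint". The recorded reason plays no part.

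On reasons, protocol 8.1.5 says that "the primary reason for not completing the trial must be specified on the end-of-trial form". Withdrawal criterion 5 in protocol 6.4 defines inadequate control as HbA1c above 7.0% at two consecutive scheduled visits after the first 26 weeks, with week 38 the first possible stop on that ground.

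**The concern.** The two documents sort the same subjects by different keys. The protocol's key is a result in the HbA1c data. The SAP's key is a reason, and its wording reads most naturally as an instruction to use the reason entered in the eCRF. The keys agree when the recorded reason matches the HbA1c criterion. They part when a subject stops with poor control as the recorded reason but without the confirmed pair of values.

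Such a stop is possible. Entry HbA1c is 7.5 to 9.0% (protocol 6.2), HbA1c is measured at weeks 16 and 26, central laboratory results go to the investigator (protocol 8.4), treatment is open-label, and subjects may withdraw at any time. If such a subject stopped at week 20, rule 2 would censor that stop, whereas a stop on the same day for nausea would be an event. An endpoint meant to count discontinuation for any reason would then leave out some discontinuations, according to a reason chosen by an unblinded investigator.

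**Working it through.** **Where each rule sends a stop before week 104**

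| SAP 3.6.12.1 rule | Situation | Result | Reachable by a stop before week 104? |
|---|---|---|---|
| 1 | stopped before week 16 | censored | yes |
| 2 | stopped between weeks 16 and 26 | censored | yes |
| 3 | no on-treatment HbA1c | censored | yes |
| 4 | two consecutive values above 7.0% from week 26 | event | yes |
| 5 | last value above 7.0%, at week 26 or later but before week 104 | event | yes |
| 6 | last value 7.0% or below, between weeks 26 and 104 | censored | yes |
| 7 | last value at week 104, no confirmed pair | censored | no |

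Five of the seven rules censor. Four of those (1, 2, 3 and 6) can apply to a stop before week 104.

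**Stops that meet criterion 5.** Two consecutive values above 7.0% from week 26 satisfy rule 4, whose text runs "taken at Week26 or later, then event has occurred with t1 as time of first measurement of" the first high value. If the second high value is also the last and falls before week 104, rule 5 applies too: "then the event has occurred with t1 as time of last available measurement and t2 as time of next visit". As a check, 100,000 subjects were simulated with independent values at each visit (mean 6.9%, SD 0.85%, protocol 17.1). Of these, 59,443 stopped before week 104 on the criterion. All 59,443 satisfied rules 4 and 5, and none satisfied rule 6. This follows from the definitions, but it confirms that the ordinary route is coded correctly.

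**An overlap.** Rule 6 does not exclude a subject who already has a confirmed pair. Two values above 7.0% followed by a later on-treatment value of 7.0% or below fit both rule 4 and rule 6. SAP Figure 1 may set the order, but it is missing from the text available here.

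**Stops recorded as poor control but not confirmed.** A last value above 7.0% at week 26 or later is still an event under rule 5. Three kinds of stop remain exposed:

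- stops before week 26 (rules 1 and 2);
- stops with no on-treatment HbA1c (rule 3);
- stops with a last value of 7.0% or below and no confirmed pair (rule 6).

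For all three, protocol 17.4.1.1 gives an event and SAP 3.6.12.1 gives a censored record.

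**Scale, using the plan's own counts.** Inputs are 1,994 randomised (protocol 17.1), and 526 and 606 control events with 200 other stops per arm (Amendment 1, section 2.11).

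- Completers: 1,994 − 526 − 606 − 400 = 462, as stated.
- Event proportions: 526/(997 − 200) = 66.0% and 606/(997 − 200) = 76.0%, as stated.
- Discontinuation events under the protocol rule: 526 + 606 + 400 = 1,532, which is 1,994 − 462.

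The exposed stops lie among the 400. Their number is not given, so the share below is an assumption.

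| Assumed share of the 400 | Events lost | Share of 1,532 |
|---|---|---|
| 0% | 0 | 0% |
| 5% | 20 | 1.3% |
| 10% | 40 | 2.6% |
| 25% | 100 | 6.5% |
| 100% (ceiling) | 400 | 26.1% |

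**The case against.** The strongest reply is that inadequate glycaemic control is a defined term. The protocol's endpoint and withdrawal sections and the opening of SAP 3.6.12.1 all give it the same two-visit meaning, with week 38 as the earliest occurrence. Read that way, a week-20 stop for poor control is a stop for another reason and counts as an event, rules 1 to 3 never apply to the first group, and the SAP split is close to the protocol's. SAP 3.6.12.2 itself names only week-104 completers as censored, so nothing suggests that censoring a discontinuer was intended.

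Much of this stands. It shows that the censoring is probably unintended and that the effect may be nil. It does not settle how the variable is built, because 3.6.12.2 does not say whether the reason is the HbA1c criterion or the eCRF entry. The response options on the end-of-trial form are not shown either.

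A reader might go further and infer that the SAP censors treatment stops in general, or that the error works against the more effective arm and costs power. The documents support neither. Only unconfirmed stops recorded with that reason are exposed. A direction would need such stops to be more frequent in one arm, and the plan gives no such imbalance: it assumes 200 other stops in each arm and the same mean HbA1c in both arms until after week 65.

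**Conclusion.** The point holds as an ambiguity with a definite consequence under one reading. If the split uses the recorded reason, unconfirmed stops attributed to inadequate control are censored. That contradicts protocol 17.4.1.1 and the SAP's own sentence limiting censoring to completers. If the term is read strictly as criterion 5, the effect is nil. Between these readings the size is unknown; the percentages above rest on assumed shares and are not estimates.

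The endpoint is supportive and is not one of the starred key endpoints in protocol 4.2.2.1. The primary analysis and the sample size do not depend on this point. It is still worth correcting, because the corrected wording is right under both readings and removes dependence on an investigator-recorded reason in an open-label trial.

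**What to change.** Replace the split by reason in SAP 3.6.12.2 with a split by result:

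> If rule 4 or rule 5 of section 3.6.12.1 gives an event, use that interval (rule 4 takes precedence over rule 6). Every other subject who stops treatment before week 104, whatever the recorded reason, has the event in (last attended on-treatment visit, next planned visit].

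The existing sentence that censors only week-104 completers can stay. The cost is this short replacement text and the matching change to the derivation of one parameter in ADTTE. No new data are needed. If criterion 5 was intended throughout, the change makes the text unambiguous without affecting how any early stop is classed.
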